HEPATOBILIARY DISOF	KDER5	Llenstebilien, die endere	
		Hepatobiliary disorders - Other (hepatitis)	
IMMUNE SYSTEM DISO			
		Allergic reaction	
		Cytokine release syndrome ²	
	ND PROCEDURAL COMPLICATION		
	Infusion related reaction		
INVESTIGATIONS			
	Alanine aminotransferase		
	increased ³		
	Alkaline phosphatase increased ³		
	Aspartate aminotransferase		
	increased		
	Blood bilirubin increased ³		
	GGT increased ³		
	Lipase increased		
	Lymphocyte count decreased		Lymphocyte count decreased (Gr 2)
	Neutrophil count decreased		
	Serum amylase increased		
	Thyroid stimulating hormone		
	increased		
METABOLISM AND NUT		 T	
	Anorexia	Tumor lysis syndrome ⁴	
	ND CONNECTIVE TISSUE DISORE	DERS	
MUSCULUSKELETAL A			
MUSCULUSKELETAL A	Arthralgia		
NERVOUS SYSTEM DIS	· · · · · · · · · · · · · · · · · · ·		

	Adverse Events with Possib tionship to CDX-1127 (varlilu (CTCAE 5.0 Term) [n= 343]		Specific Protocol Exceptions to Expedited Reporting (SPEER)
Likely (>20%)	Less Likely (<=20%)	Rare but Serious (<3%)	
		Nervous system disorders - Other (peripheral sensorimotor neuropathy)	
		Paresthesia	
		Peripheral sensory neuropathy	
RESPIRATORY, THORACIC	AND MEDIASTINAL DISORD	ERS	
		Pneumonitis	
SKIN AND SUBCUTANEOUS	TISSUE DISORDERS		
Pruritus			Pruritus (Gr 2)
Rash maculo-papular			Rash maculo-papular (Gr 2)
		Skin hyperpigmentation	
		Skin hypopigmentation	

¹This table will be updated as the toxicity profile of the agent is revised. Updates will be distributed to all Principal Investigators at the time of revision. The current version can be obtained by contacting [contact]. Your name, the name of the investigator, the protocol and the agent should be included in the e-mail.

²Symptoms of cytokine release syndrome (CRS) and/or allergic reaction may include chills, fever, fatigue, flushing, bronchospasm, and hypotension. In some cases, disseminated intravascular coagulation (DIC), capillary leak syndrome (CLS), and hemophagocytic lymphohistiocytosis/macrophage activation syndrome (HLH/MAS) have been reported in the setting of CRS.

³Symptoms of hepatic dysfunction may include Alanine aminotransferase increased, Alkaline phosphatase increased, Aspartate aminotransferase increased, Blood bilirubin increased, and GGT increased under the INVESTGATIONS SOC.

⁴Tumor lysis syndrome is defined as a massive overload of potassium, phosphate, uric acid, plus hypocalcemia, potentially causing lethal cardiac arrhythmias and/or renal failure.

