		Respiratory, thoracic and mediastinal disorders - Other (bronchiolitis obliterans with organizing pneumonia) ³	
SKIN AND SUBCUTANEO	US TISSUE DISORDERS		
		Erythema multiforme ³	
	Pruritus ³		Pruritus ³ (Gr 2)
	Rash maculo-papular ³		Rash maculo-papular ³ (Gr 2)
		Skin and subcutaneous tissue disorders - Other (bullous pemphigoid)	
	Skin and subcutaneous tissue disorders - Other (Sweet's Syndrome) ³		
	Skin hypopigmentation ³		
		Stevens-Johnson syndrome	
		Toxic epidermal necrolysis	

¹This table will be updated as the toxicity profile of the agent is revised. Updates will be distributed to all Principal Investigators at the time of revision. The current version can be obtained by contacting [contact]. Your name, the name of the investigator, the protocol and the agent should be included in the e-mail.

²Pericardial tamponade may be related to possible inflammatory reaction at tumor site.

³Nivolumab being a member of class of agents involved in the inhibition of "immune checkpoints", may result in severe and possibly fatal immune-mediated adverse events probably due to T-cell activation and proliferation. This may result in autoimmune disorders that can include (but are not limited to) autoimmune hemolytic anemia, acquired anti-factor VIII immune response, autoimmune aseptic meningitis, autoimmune hepatitis, autoimmune nephritis, autoimmune neuropathy, autoimmune thyroiditis, bullous pemphigoid, exacerbation of Churg-Strauss Syndrome, drug rash with eosinophilia systemic symptoms [DRESS] syndrome, facial nerve disorder (facial nerve paralysis), limbic encephalitis, hepatic failure, pure red cell aplasia, pancreatitis, ulcerative and hemorrhagic colitis, endocrine disorders (e.g., autoimmune thyroiditis, hyperthyroidism, hypothyroidism, autoimmune hypophysitis/hypopituitarism, thyrotoxicosis, and adrenal insufficiency), sarcoid granuloma, myasthenia gravis, polymyositis, and Guillain-Barre syndrome.

⁴Pancreatitis may result in increased serum amylase and/or more frequently lipase.

⁵Cytokine release syndrome may manifest as hemophagocytic lymphohistiocytosis with accompanying fever and pancytopenia.

⁶Complications including hyperacute graft-versus-host disease (GVHD), some fatal, have occurred in patients receiving allo stem cell transplant (SCT) after receiving Nivolumab. These complications may occur despite intervening therapy between receiving Nivolumab and allo-SCT.

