7.3.4 Additional Protocol-Specific Expedited Adverse Event Reporting Exclusions

For this protocol only, the AEs/grades listed below *do not* require expedited reporting via CTEP-AERS. However, they still must be reported through the routine reporting mechanism (Section 7.4):

CTCAE SOC	Adverse Event	CTCAE Grade at which the event will not require expedited reporting ¹
Investigations	Neutrophil count decreased	\leq Grade 4
	Platelet count decreased	\leq Grade 4
	White blood count	\leq Grade 4
	Lymphocyte count decreased	≤ Grade 4
Blood and lymphatic system disorders	Anemia	≤ Grade 4

¹ These exceptions only apply if the adverse event does not result in hospitalization. If the adverse event results in hospitalization, then the standard expedited adverse events reporting requirements must be followed.

Specific protocol exceptions to expedited reporting should be reported expeditiously by investigators **ONLY** if they exceed the expected grade of the event.

The following hospitalizations are not considered to be SAEs because there is no "adverse event" (*i.e.*, there is no untoward medical occurrence) associated with the hospitalization:

- Hospitalizations for respite care
- Planned hospitalizations required by the protocol
- Hospitalization planned before informed consent (where the condition requiring the hospitalization has not changed post study drug administration)
- Hospitalization for elective procedures unrelated to the current disease and/or treatment on this trial
- Hospitalization for administration of study drug or insertion of access for administration of study drug
- Hospitalization for routine maintenance of a device (*e.g.*, battery replacement) that was in place before study entry
- Hospitalization, or other serious outcomes, for signs and symptoms of progression of the cancer.

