13.7 Adverse Event Stopping Rule

The stopping rule applies to each group independently.

The stopping rule specified below is based on the knowledge available at study development. We note that the rule may be adjusted in the event of either (1) the study re-opening to accrual or (2) at any time during the conduct of the trial and in consideration of newly acquired information regarding the adverse event profile of the treatments under investigation. The study team may choose to suspend accrual because of unexpected adverse event profiles that have not crossed the specified rule below.

Accrual will be temporarily suspended to both groups if at any time we observe events considered relevant to the study treatment (defined as any adverse events except those receiving the "unrelated" attribution) that satisfy one of the following in either of the groups (evaluated in each group separately):

- if 4 or more patients in the first 20 treated patients in the group experience a grade 4 or higher non-hematologic adverse event relevant to treatment.
- if after the first 20 patients have been treated, 20% of all patients in the group experience a grade 4 or higher non-hematologic adverse event relevant to treatment.

We note that we will review grade 4 and 5 adverse events deemed "unrelated" to verify their attribution and to monitor the emergence of a previously unrecognized treatment-related adverse event.

REFERENCES

Ai, W. Z. *et al.* (2009). Follicular lymphoma B cells induce the conversion of conventional CD4 + T cells to T-regulatory cells. *Int. J. Cancer* **124**, 239–244.

Ansell, S. M. *et al.* (2014). PD-1 Blockade with Nivolumab in Relapsed or Refractory Hodgkin's Lymphoma. *N Engl J Med* **372**, 311–319.

Ansell, S. M. *et al.* (2014). Phase I evaluation of an agonist anti-CD27 human antibody (CDX-1127) in patients with advanced hematologic malignancies. *J Clin Oncol* **32**, abstr 3024.

Brahmer, J.R., L. Horn, S.J. Antonia, *et al.* (2013). Survival and long-term follow-up of the phase I trial of nivolumab (Anti-PD-1; BMS-936558; ONO-4538) in patients (pts) with previously treated advanced non-small cell lung cancer (NSCLC). *J Clin Oncol.* 31:A8030.

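### The adverse event stopping rule excludes an undefined class of hematologic events with no exception for deaths, so whether a fatal or immune-mediated blood disorder counts depends on how it is coded

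*Combined protocol and SAP*

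**What the plan says.** Section 13.7 applies the rule to each group separately and suspends accrual to both groups if either one meets it. The first limb is 4 or more of the first 20 treated patients who "experience a grade 4 or higher non-hematologic adverse event relevant to treatment". The second limb takes over after 20 patients: it sets the limit at 20% of everyone treated in the group and uses the same event criterion. Relevant means any attribution other than unrelated. There is no limb for deaths, none for hematologic events, and no definition of the excluded class. The same section leaves room for judgment: "The study team may choose to suspend accrual because of unexpected adverse event profiles that have not crossed the specified rule below".

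The risk lists in Section 7.1.1 name blood disorders for both drugs. Footnote 3 of the nivolumab list describes severe and possibly fatal immune-mediated events and continues: "This may result in autoimmune disorders that can include (but are not limited to) autoimmune hemolytic anemia, acquired anti-factor VIII immune response". It also names pure red cell aplasia. Footnote 5 adds hemophagocytic lymphohistiocytosis (HLH) with pancytopenia as a form of cytokine release syndrome. For varlilumab the support is thinner. Footnote 2 of Section 7.1.1.1 says that, in some cases, disseminated intravascular coagulation (DIC), capillary leak syndrome and "hemophagocytic lymphohistiocytosis/macrophage activation syndrome (HLH/MAS) have been reported in the setting of CRS".

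Elsewhere the protocol exempts cytopenias more narrowly. The Section 7.3.4 table waives expedited reporting for five named terms, up to grade 4, and adds: "These exceptions only apply if the adverse event does not result in hospitalization".

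**The concern.** Excluding expected laboratory cytopenias from a safety boundary in lymphoma is sensible. Section 13.7 goes further: it excludes a whole class by name, at every grade, without saying what belongs to it. Two things follow. A death that is relevant to treatment and classed as hematologic adds zero to the only numerical safety rule in the plan. And the same clinical event may or may not count, depending on the term the site chooses. At stake is whether the boundary does its job for a two-antibody immune combination whose own risk lists include immune-mediated blood disorders.

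**Working it through.** **1. The boundary.** 4/20 = 20%, so the two limbs agree at patient 20. No operating characteristics are stated, so there is no planned figure to reproduce beyond this.

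**2. What is counted under each way of classing events.** Section 13.7 prescribes neither.

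| Event | Classed by clinical nature | Classed by organ class of the reported term |
|---|---|---|
| Autoimmune hemolytic anemia, anti-factor VIII response, red cell aplasia | Hematologic: not counted | Counted if reported as autoimmune disorder (an immune system term in 7.1.1.2); not counted if reported under a blood term |
| DIC, or HLH with or without macrophage activation syndrome (HLH/MAS) | Arguable | Counted if reported as cytokine release syndrome (an immune system term); not counted if reported under a blood term |
| Grade 4 lymphocyte decrease | Hematologic: not counted | Counted, because 7.3.4 files it under Investigations |
| Fatal anemia relevant to treatment | Hematologic: not counted | Not counted (7.3.4 files anemia under blood and lymphatic disorders) |

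The last row goes uncounted on either reading. The other rows turn on coding.

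**3. Effect on a borderline group.** Suppose three of the first 20 patients have a counted event and a fourth dies of a relevant event classed as hematologic. As written the count is 3/20 = 15%: no pause. If the death counts, it is 4/20 = 20%: pause. With no other counted event, one such death gives 1/20 = 5%, so it would not cause a pause under either wording.

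**4. Change in the chance of a pause.** Let p be the true proportion of patients with a counted event. For the first limb,

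P(X ≥ 4) = 1 − Σ (k = 0 to 3) C(20, k) p^k (1 − p)^(20 − k).

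The documents give no grade 4–5 rates, so base rates of 10% and 12% and additions of 1 or 2 percentage points are assumptions, taken as additive.

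- p = 0.10: 1 − (0.1216 + 0.2702 + 0.2852 + 0.1901) = 13.3%
- p = 0.11: 17.1%
- p = 0.12: 1 − (0.0776 + 0.2115 + 0.2740 + 0.2242) = 21.3%
- p = 0.13: 25.7%
- p = 0.14: 30.4%

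So the first limb moves from 13% to 17–21% on the 10% base, and from 21% to 26–30% on the 12% base.

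**5. Both limbs to 48 patients.** I updated the count patient by patient and stopped at 4 within the first 20, or at 20% or more of n afterwards. This assumes a check after every patient. The chance that one group crosses is 17.1% at 10%, 22.3% at 11%, 28.1% at 12%, 34.3% at 13% and 40.7% at 14%. The shift has the same direction and is somewhat larger.

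**The case against.** The strongest reply is that many of these events may already count. Footnote 3 is attached to autoimmune disorder under immune system disorders, and the blood section of the nivolumab list has only anemia, without that footnote. Cytokine release syndrome is an immune system term in both lists, and thrombotic microangiopathy is listed there too. This stands. A reader might infer that a whole class of immune toxicity can never trigger the rule, but the documents do not support that. They show that the classification is left open.

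Second, a reader might infer that several patients could die of hemolysis without anyone acting. The documents do not support that either. Every death needs expedited reporting whatever its cause (7.3.3), toxicity enters any decision to terminate (13.1.3), the principal investigator and statistician can see the data at all times (12.1), the team may suspend accrual below the boundary (13.7), and grade 3 or higher hematologic events are compared between groups (13.4.3.1). Four fatal cases in 20 would also be very unlikely: even at a 3% rate with every case fatal, P(X ≥ 4) is 0.3%. What survives is that none of these safeguards has a threshold, and the review of grade 4 and 5 events in 13.7 covers only those deemed unrelated.

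Third, one could show a larger effect by assuming 5% severe immune blood events on a 12% base, which moves the first limb from 21% to 45% (p = 0.17). No passage supports 5%. Both lists place cytokine release syndrome in the below-3% band, and the nivolumab list does the same for autoimmune disorder. Those bands are for each agent, not this combination, so a higher rate is possible but would be conjecture.

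Finally, excluding cytopenias is a reasoned choice: lymphopenia is expected with both drugs (6.1), and relevance extends to events judged unlikely to be related. That supports a named list of exclusions. It does not support excluding deaths.

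**Conclusion.** The point holds as a gap in definition and in the handling of deaths. Section 13.7 counts only non-hematologic events of grade 4 or higher, does not define the term and makes no exception for grade 5. A treatment-relevant death or immune blood disorder classed as hematologic does not count toward 4 of 20 or 20%. Whether hemolysis, DIC or HLH/MAS counts depends on coding.

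The size is modest. Under assumed additions of 1–2 percentage points, the chance of meeting the first limb rises by about 4 to 8 points on a 10% base and 4 to 9 points on a 12% base. The reading of the text does not depend on those rates; the percentages do. The gain is that the boundary gives the same answer however an event is coded, and that no relevant death is left out.

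**What to change.** In both limbs of Section 13.7, replace the non-hematologic criterion with the following:

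- Count any grade 5 adverse event relevant to treatment, whatever its class.
- Count any grade 4 adverse event relevant to treatment, except a named list of laboratory cytopenias: the five terms in the Section 7.3.4 table (neutrophils, platelets, white cells, lymphocytes, anemia) plus CD4 lymphocytes decreased. The last term is absent from that table but is exempt from expedited reporting through grade 4 in the nivolumab list, so copying the table alone would bring it into the count.
- State that events reported as autoimmune disorder, cytokine release syndrome or another immune-mediated diagnosis count.

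Keep the thresholds and the definition of relevant. Progression deaths are unaffected: Section 7.3.3 reports them under general disorders, which is already non-hematologic.

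The cost is a short rewording and a somewhat higher chance of a temporary accrual pause, as shown above. The change makes a hematologic death count; it does not make one such death sufficient for a pause. If the sponsor wants that, a separate grade 5 criterion would be needed. At assumed rates of relevant hematologic death of 1% or 2%, the chance of at least one in a group, 1 − (1 − rate)^n, is 18% or 33% in 20 patients and 38% or 62% in 48. Such a criterion would therefore pause accrual far more often.

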7.2 Adverse Event Characteristics

- CTCAE term (AE description) and grade: The descriptions and grading scales found in the revised NCI Common Terminology Criteria for Adverse Events (CTCAE) version 5.0 will be utilized for AE reporting. All appropriate treatment areas should have access to a copy of the CTCAE version 5.0. A copy of the CTCAE version 5.0 can be downloaded from the CTEP web site http://ctep.cancer.gov/protocolDevelopment/electronic_applications/ctc.htm.
- For expedited reporting purposes only:
 - AEs for the agent that are **bold** and *italicized* in the CAEPR (*i.e.*, those listed in the SPEER column, Section 7.1.1) should be reported through CTEP-AERS only if the grade is above the grade provided in the SPEER.
 - Other AEs for the protocol that do not require expedited reporting are outlined in section 7.3.4.
- **Attribution** of the AE:
 - Definite The AE *is clearly related* to the study treatment.
 - Probable The AE is likely related to the study treatment.
 - Possible The AE *may be related* to the study treatment.
 - Unlikely The AE is doubtfully related to the study treatment.
 - Unrelated The AE is clearly NOT related to the study treatment.

Although standard AE attributions will be collected and recorded as part of this study all adverse events will be considered relevant to study treatment unless clearly determined to be unrelated to the drugs and therefore classified as unrelated.

7.3 Expedited Adverse Event Reporting

7.3.1 Expedited AE reporting for this study must use CTEP-AERS (CTEP Adverse Event Reporting System), accessed via the CTEP Web site (https://eapps-ctep.nci.nih.gov/ctepaers). The reporting procedures to be followed are presented in the "NCI Guidelines for Investigators: Adverse Event Reporting Requirements for DCTD (CTEP and CIP) and DCP INDs and IDEs" which can be downloaded from the CTEP Web site (http://ctep.cancer.gov/protocolDevelopment/electronic_applications/adverse_events.htm)

). These requirements are briefly outlined in the tables below (Section 7.3.3).

In the rare occurrence when Internet connectivity is lost, a 24-hour notification is to be made to CTEP by telephone at [contact]. Once Internet connectivity is restored, the 24-hour notification phoned in must be entered electronically into CTEP-AERS by the original submitter at the site.

7.3.2 Distribution of Adverse Event Reports

CTEP-AERS is programmed for automatic electronic distribution of reports to the following individuals: Principal Investigator and Adverse Event Coordinator(s) (if applicable) of the Corresponding Organization or Lead Organization, the local treating physician, and the Reporter and Submitter. CTEP-AERS provides a copy feature for other e-mail recipients.

7.3.3 Expedited Reporting Guidelines

Use the NCI protocol number and the protocol-specific patient ID assigned during trial registration on all reports.

Note: A death on study requires both routine and expedited reporting, regardless of causality. Attribution to treatment or other cause must be provided.

"Death due to progressive disease should be reported as Grade 5 "Disease progression" in the system organ class (SOC) "General disorders and administration site conditions." Evidence that the death was a manifestation of underlying disease (*e.g.*, radiological changes suggesting tumor growth or progression: clinical deterioration associated with a disease process) should be submitted.

Phase 1 and Early Phase 2 Studies: Expedited Reporting Requirements for Adverse Events that Occur on Studies under an IND/IDE within 30 Days of the Last Administration of the Investigational Agent/Intervention ^{1, 2}

FDA REPORTING REQUIREMENTS FOR SERIOUS ADVERSE EVENTS (21 CFR Part 312)

NOTE: Investigators **MUST** immediately report to the sponsor (NCI) **ANY** Serious Adverse Events, whether or not they are considered related to the investigational agent(s)/intervention (21 CFR 312.64)

An adverse event is considered serious if it results in ANY of the following outcomes:

- 1) Death
- 2) A life-threatening adverse event
- An adverse event that results in inpatient hospitalization or prolongation of existing hospitalization for ≥ 24 hours
- 4) A persistent or significant incapacity or substantial disruption of the ability to conduct normal life functions
- 5) A congenital anomaly/birth defect.
- 6) Important Medical Events (IME) that may not result in death, be life threatening, or require hospitalization may be considered serious when, based upon medical judgment, they may jeopardize the patient or subject and may require medical or surgical intervention to prevent one of the outcomes listed in this definition. (FDA, 21 CFR 312.32; ICH E2A and ICH E6).

ALL SERIOUS adverse events that meet the above criteria MUST be immediately reported to the NCI via electronic submission within the timeframes detailed in the table below.

Hospitalization	Grade 1 and Grade 2 Timeframes	Grade 3-5 Timeframes
Resulting in Hospitalization ≥ 24 hrs	10 Calendar Days	24-Hour 5 Calendar
Not resulting in Hospitalization ≥ 24 hrs	Not required	Days

NOTE: Protocol specific exceptions to expedited reporting of serious adverse events are found in the Specific Protocol Exceptions to Expedited Reporting (SPEER) portion of the CAEPR.

Expedited AE reporting timelines are defined as:

- "24-Hour; 5 Calendar Days" The AE must initially be submitted electronically within 24 hours of learning of the AE. followed by a complete expedited report within 5 calendar days of the initial 24-hour report.
- "10 Calendar Days" A complete expedited report on the AE must be submitted electronically within 10 calendar days of learning of the AE.

¹Serious adverse events that occur more than 30 days after the last administration of investigational agent/intervention and have an attribution of unlikely, possible, probable, or definite require reporting as follows: **Expedited 24-hour notification followed by complete report within 5 calendar days for:**

- All Grade 3, 4, and Grade 5 AEs
- Expedited 10 calendar day reports for:
 - Grade 2 AEs resulting in hospitalization or prolongation of hospitalization

²For studies using PET or SPECT IND agents, the AE reporting period is limited to 10 radioactive half-lives, rounded UP to the nearest whole day, after the agent/intervention was last administered. Footnote "1" above applies after this reporting period.

Effective Date: May 5, 2011

